5.2. Eliciting and Reporting Adverse Events

The investigator will periodically assess subjects for the occurrence of AEs. To avoid bias in eliciting AEs, subjects should be asked the following nonleading question: "How have you felt since your last visit?" All AEs (serious and nonserious) reported by the subject must be recorded on the source documents and eCRFs provided by the sponsor or designee.

In addition, INC Research (refer to [Appendix 2](#)) must be notified immediately by telephone or fax of any **immediately reportable events** according to the procedure outlined below in [Section 5.3](#). Special attention should be paid to recording hospitalization and concomitant medications.

5.3. Immediately Reportable Events (IRE)

The investigator must immediately report within 24 hours after either the investigator or site personnel become aware of any **SAE or potential Hy's law cases** (refer to [Section 5.4](#)) by telephone or by fax to the sponsor or designee, as outlined in [Appendix 2](#). An IRE form must be completed and sent by fax or overnight courier to the sponsor. (Note: the IRE form is NOT the AE eCRF.)

Protocol 331-12-283

Nonserious events that require discontinuation of the IMP (including laboratory abnormalities) should be reported to the sponsor within 3 working days. The IRE form must be completed and sent by fax or overnight courier to the sponsor.

Subjects experiencing SAEs should be followed clinically until their health has returned to baseline status or until all parameters have returned to normal or have otherwise been explained. It is expected that the investigator will provide or arrange appropriate supportive care for the subject.

5.4. Potential Hy's Law Cases

For subjects that experience an elevation in AST or ALT that is ≥ 3 times the ULN, a total bilirubin level should also be evaluated. If the total bilirubin is ≥ 2 times the ULN, confirmatory repeat laboratory samples should be drawn within 48 to 72 hours of the initial draw. If these values are confirmed, trial personnel will complete an IRE form with all values listed and also report the event as an AE on the eCRF. Please note: if the subject was enrolled into the trial with non-exclusionary elevated transaminase levels at baseline, please discuss any potential drug-induced liver injury events with the medical monitor.

5.5. Pregnancy

Women of childbearing potential and men who are sexually active must use an effective method of birth control during the course of the trial and for at least 30 days after the last dose in a manner such that risk of failure is minimized. Unless the subject is sterile (ie, women who have had an oophorectomy and/or hysterectomy or have been postmenopausal for at least 12 consecutive months; or men who have had orchiectomy) or remains abstinent, two of the following precautions must be used: vasectomy, tubal ligation, vaginal diaphragm, intrauterine device, birth control pills, birth control depot injection, birth control implant, condom or sponge with spermicide, or any other method approved by the medical monitor. Any single method of birth control, including vasectomy and tubal ligation, may fail, leading to pregnancy.

Before enrolling women of childbearing potential in this clinical trial, investigators must review guidelines about their participation in this trial. The topics should generally include:

- General information
- Informed consent
- Pregnancy prevention information

Protocol 331-12-283

- Drug interactions with hormonal contraceptives
- Contraceptives in current use
- Guidelines for the follow-up of a reported pregnancy

Prior to trial enrollment, women of childbearing potential must be advised of the importance of avoiding pregnancy during trial participation and the potential risk factors for an unintentional pregnancy. The subject must sign an ICF stating that the above-mentioned risk factors and the consequences were discussed with her.

During the trial, all women of childbearing potential should be instructed to contact the investigator immediately if they suspect they might be pregnant (eg, missed or late menstrual cycle).

If a subject or investigator suspects that the subject may be pregnant prior to IMP administration, the IMP administration must be withheld until the results of serum pregnancy tests are available. If the pregnancy is confirmed, the subject must not receive the IMP and must not be enrolled in the trial. If pregnancy is suspected while the subject is taking the IMP, the IMP must be withheld immediately (if reasonable, taking into consideration any potential withdrawal risks) until the result of the pregnancy is known. If pregnancy is confirmed, the IMP will be permanently discontinued in an appropriate manner (eg, dose tapering if necessary for subject safety) and the subject withdrawn from the trial. Exceptions to trial discontinuation may be considered for life-threatening conditions only after consultation as indicated in [Appendix 2](#).

The investigator must immediately notify the sponsor (or sponsor's designee) of any pregnancy associated with IMP exposure, including at least 30 days after the last dose for female subjects and the female partner of a male subject and record the event on the IRE form and forward it to the sponsor (or sponsor's designee).

Protocol-required procedures for trial discontinuation and follow-up must be performed on the subject unless contraindicated by pregnancy (eg, x-ray studies). Other appropriate pregnancy follow-up procedures should be considered if indicated. In addition, the investigator must report to the sponsor (or sponsor's designee), on appropriate Pregnancy Surveillance form(s), follow-up information regarding the course of the pregnancy, including perinatal and neonatal outcome. Infants will be followed for a minimum of 6 months.

Protocol 331-12-283

5.6. Procedure for Breaking the Blind

The investigator is encouraged to contact the sponsor/Clinical Research Organization (CRO) medical advisor to discuss their rationale for unblinding. However, to prevent delays to the investigator or medical personnel responding to a potentially emergent situation, unblinding of the IMP will not be dependent upon the investigator receiving approval from the sponsor/CRO medical monitor (ie, the investigator will be able to obtain the code break information independent of the sponsor/CRO medical advisor). The investigator must contact the sponsor/CRO medical advisor by telephone with an explanation of the need for opening the treatment assignment code within 24 hours of opening the code. If the blind is broken, the clinical safety and pharmacovigilance department listed in [Appendix 2](#) will be notified immediately. Documentation of breaking the blind should be recorded in the subject's medical record with the date and time the blind was broken and the names of the personnel involved. Once the blind is broken for a given subject, that subject may not reinitiate treatment with the IMP.

5.7. Follow-up of Adverse Events

5.7.1. Follow-up of Nonserious Adverse Events

Nonserious AEs that are identified on the last scheduled contact must be recorded on the AE eCRF with the current status noted. All nonserious events that are ongoing at this time will be recorded as ongoing on the eCRF.

5.7.2. Follow-up of Post-Trial Serious Adverse Events

All SAEs that are identified on the last scheduled contact must be recorded on the AE eCRF page and reported to the sponsor according to the reporting procedures outlined in [Section 5.3](#). This may include unresolved previously reported SAEs or new SAEs. The investigator will follow SAEs until the events are resolved or the subject is lost to follow-up. Resolution means the subject has returned to the baseline state of health, or the investigator does not expect any further improvement or worsening of the subject's condition. The investigator will continue to report any significant follow-up information to OPDC up to the point the event has been resolved.

This trial requires that subjects be actively monitored for SAEs up to 30 days after discharge from the trial.

Protocol 331-12-283

5.7.3. Follow-up and Reporting of Serious Adverse Events Occurring after Last Scheduled Contact

Any new SAEs reported by the subject to the investigator that occur after the last scheduled contact and are determined by the investigator to be reasonably associated with the use of the IMP, should be reported to OPDC. This may include SAEs that are captured on follow-up telephone contact or at any other time point after the defined trial period (ie, up to last scheduled contact). The investigator should follow related SAEs identified after the last scheduled contact until the events are resolved or the subject is lost to follow-up. The investigator should continue to report any significant follow-up information to OPDC up to the point the event has been resolved.

5.7.4.

CCI

6. Pharmacokinetic Analysis

Pharmacokinetic samples will be analyzed for brexpiprazole (OPC-34712) and its metabolite(s) and descriptive statistics will be calculated. No formal statistical comparisons are planned. A separate population or pharmacokinetic/pharmacodynamic modeling may be performed using the data from this trial and other trials.

7. Statistical Analysis

7.1. Sample Size

The sample size was calculated based on the treatment effect of 6.5 points with a standard deviation (SD) of 16.5 in the change from baseline (Day 0 visit) to the end of the double-blind treatment period (Week 12 visit) in the CMAI total score, to achieve 85% power at a 2-sided alpha level of 0.05. This results in 117 subjects in each of the groups (ie, brexpiprazole 1 mg/day, brexpiprazole 2 mg/day, and placebo). After allowance of 10% non-evaluable subjects, the total number of subjects to be randomized is 132 per treatment arm. The sample size was estimated based on a 1:1:1 randomization ratio (brexpiprazole 1 mg/day, brexpiprazole 2 mg/day, placebo). CCI

Protocol 331-12-283

7.4. Efficacy Analyses

7.4.1. Primary Efficacy Analysis

The primary endpoint will be analyzed using an MMRM model. The primary efficacy outcome measure is the mean change from baseline (Day 0 visit) to the end of the double-blind treatment period (Week 12 visit) in the CMAI total score. The primary statistical comparisons of interest are brexpiprazole 2 mg/day versus placebo and brexpiprazole 1 mg/day versus placebo. The null hypotheses of these comparisons are that there is no difference between the brexpiprazole treatment groups and placebo in change from baseline to endpoint in CMAI total score. To protect the experiment-wise 2-sided alpha level at 0.05 when making 2 comparisons of brexpiprazole doses versus placebo, the statistical testing will be carried out using a hierarchical testing procedure in the order of 1) comparison of 2 mg/day brexpiprazole versus placebo and 2) comparison of 1 mg/day brexpiprazole versus placebo. Thus, if the test yields a statistically significant result at 0.05 (2-sided) for the comparison of 2 mg/day brexpiprazole versus placebo, then the comparison of 1 mg/day brexpiprazole versus placebo will be tested at an alpha level of 0.05 (2-sided).

The statistical comparison will be performed by the MMRM analysis with an unstructured variance covariance matrix for the repeated measures in which the change from baseline (Day 0 visit) in CMAI total score (at Weeks 2, 4, 6, 8, 10, and 12) will be the dependent variable based on the OC dataset. The model will include fixed class-effect terms for treatment, trial center, visit week, and an interaction term of treatment by visit week and include the interaction term of baseline values of CMAI total score by visit week as a covariate. The primary comparison between brexpiprazole and the placebo arm at Week 12 will be estimated as the difference between least squares (LS) means from the interaction term of treatment by visit week utilizing the computing software SAS procedure PROC MIXED.

CCI

The primary analysis CCI will be performed on the Efficacy Sample.

Protocol 331-12-283

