- Urine will be collected from all potential subjects for urinalysis and urine screen(s) for drugs of abuse. Subjects positive for cocaine, marijuana, or other illicit drugs are not eligible to be retested or rescreened. Subjects with a positive drug screen resulting from use of prescription or OTC medications or products may be retested (the evaluation may be repeated within the screening period) or rescreened once for participation in the trial after consent of the medical monitor.
- Urine albumin-to-creatinine ratio (ACR) will be determined only for subjects with insulin-dependent diabetes mellitus (IDDM) (must be < 30 mg/g; calculated as urine albumin [mg/dL]/urine creatinine [g/dL]).

Protocol 331-12-283

- A urine pregnancy test will be performed for all women of childbearing potential. All positive results must be confirmed by a serum pregnancy test. Subjects with positive urine and serum test results will be excluded from the trial.
- An adequately trained and experienced clinician will confirm the diagnosis of probable Alzheimer's disease using the NINCDS-ADRDA criteria.
- An adequately trained and experienced physician who performs the neurological examination will complete the Hachinski Ischemic Scale (Rosen Modification).
- A qualified and certified rater will administer the CMAI and NPI-NH (for institutionalized subjects) or NPI/NPI-NH (for non-institutionalized subjects) to the identified caregiver.
- An adequately trained and experienced clinician will administer the CGI-S.
- An adequately trained and experienced clinician will administer the MMSE.
- CCI [REDACTED]
- AEs will be recorded, beginning with the signing of the ICF.
- Concomitant medications will be recorded.
- CCI [REDACTED]
- The subject's caregiver and/or facility staff will complete a paper diary daily (if possible) after the ICF is signed, continuing through Week 12/ET.

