7.4.2. Key Secondary Efficacy Analysis

The key secondary efficacy variable is the change from baseline to endpoint in the CGI-S score, as related to agitation. It will be analyzed by the same statistical methodology specified for the analysis of the primary efficacy variable, based on the ITT population. In order to control the overall type I error rate for this key secondary efficacy analysis, a hierarchical testing procedure will be used so that the overall experiment-wise type I error rate is maintained at 0.05. Thus, if the primary efficacy analysis for the CMAI total score (as described in [Section 7.4.1](#)) yields a statistically significant result at 0.05 (2-sided) for both of the comparisons of brexpiprazole 1 mg/day and 2 mg/day versus placebo, then the corresponding comparison for this key secondary efficacy variable (CGI-S score) will be tested at an alpha level of 0.05 (2-sided) using another hierarchical testing procedure in the order of brexpiprazole 2 mg/day versus placebo and brexpiprazole 1 mg/day versus placebo. Thus, brexpiprazole 1 mg/day versus placebo will be tested only if brexpiprazole 2 mg/day versus placebo reaches significance at 0.05 (2-sided) for this key secondary efficacy variable.

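### The primary MMRM is valid, but it leaves the screening CMAI unused; adding it by visit is a nearly free, probably small gain in precision

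*Protocol*

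**What the plan says.** **Model.** Protocol Section 7.4.1, repeated in the synopsis, fixes an MMRM for change from Day 0 at Weeks 2, 4, 6, 8, 10 and 12. Its class effects are treatment, trial center, visit week and treatment by visit week. The only CMAI covariate comes from the instruction to "include the interaction term of baseline values of CMAI total score by visit week as a covariate".

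**Data collected.** Table 3.7-1 schedules the CMAI and the CGI-S at both screening and baseline. For screening, Section 3.7.1.1 says: "A qualified and certified rater will administer the CMAI and NPI-NH (for institutionalized subjects". Section 3.7.1.2 sets the same rater requirement for Day 0.

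**Key secondary variable.** Section 7.4.2 says of the CGI-S change: "It will be analyzed by the same statistical methodology specified for the analysis of the primary efficacy variable". It therefore takes over the same covariate structure.

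**Planning figures.** Section 7.1: "The sample size was calculated based on the treatment effect of 6.5 points with a standard deviation (SD) of 16.5", "to achieve 85% power at a 2-sided alpha level of 0.05". The SD is described as that of the change from Day 0 to Week 12. No correlation and no credit for covariate adjustment is stated.

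**The concern.** A single CMAI is a caregiver-informed frequency rating over two weeks, so it carries rating error and short-term fluctuation. A second score on the same scale, taken before randomization under the same rater requirements, can explain Week 12 variance that the Day 0 score misses. Because it precedes randomization, adding it as a covariate does not bias the treatment contrast, and the endpoint stays change from Day 0.

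At stake is the standard error of the two primary comparisons. If the screening score carries any information beyond Day 0, both standard errors are slightly larger than they need be. The covariate set is written into the Protocol, so this is a choice the document has made and not a detail left to the SAP. A change has to be made before unblinding.

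**Working it through.** **1. The plan's own figure.** Inputs from Section 7.1: difference 6.5, SD 16.5, two-sided alpha 0.05, power 85%, equal allocation. The normal approximation gives 116 per arm. The two-sample t-test (noncentral t) gives 84.8% power at 116 and 85.1% at 117, so the stated 117 is reproduced. Dividing by 0.9 gives 117/0.9 = 130; the plan randomizes 132, which leaves 132 × 0.9 = 118.8 evaluable. The sample size is sound.

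**2. Variance ratio.** Let a = corr(Day 0, Week 12), b = corr(screening, Day 0) and c = corr(screening, Week 12). The partial correlation of screening with Week 12 given Day 0 is

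p = (c − ab) / √[(1 − a²)(1 − b²)],

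and the residual variance with both scores, divided by that with Day 0 alone, is 1 − p². This cannot exceed 1. None of a, b or c is in the Protocol; all values below are assumptions.

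For a = 0.5 and b = 0.8 the denominator is √(0.75 × 0.36) = 0.520.

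| c | p | Variance cut |
|---|---|---|
| 0.50 (screening predicts as well as Day 0) | 0.10/0.520 = 0.192 | 3.7% |
| 0.45 | 0.05/0.520 = 0.096 | 0.9% |
| 0.40 (= ab) | 0 | 0% |

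Over a from 0.4 to 0.6 and b from 0.7 to 0.9, with c between ab and a, the cut runs from 0% to 9.9%. The top value is at a = c = 0.6, b = 0.7: p = 0.18/√(0.64 × 0.51) = 0.315, p² = 0.099.

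**3. Power at 117 per arm.** Noncentral t, 232 degrees of freedom, noncentrality 6.5/(s√(2/117)). Center effects and missing visits are ignored.

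*Reading A: 16.5 is the residual SD after Day 0 adjustment.*
- Day 0 only: s = 16.5, power 85.1%.
- Adding screening, c = 0.50: s = 16.5 × √0.963 = 16.19, power 86.4%.
- Adding screening, c = 0.45: power 85.4%.
- Top of the range (9.9% cut): power 88.5%.

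*Reading B: 16.5 is the SD of change, as Section 7.1 states.* With equal variances at Day 0 and Week 12, Var(change) = 2σ²(1 − a). At a = 0.5 this gives σ = 16.5, and the Day 0-adjusted residual SD is 16.5 × √0.75 = 14.29.
- Day 0 only: s = 14.29, power about 93.4%.
- Adding screening, c = 0.50: s = 14.29 × √0.963 = 14.02, power about 94.2%.
- Adding screening, c = 0.45: power rises by 0.2 points.

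In subjects, a 3.7% variance cut is worth about 0.037 × 132 ≈ 5 per arm.

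**The case against.** **The plan contains no mistake.** Adjusting a change score for its Day 0 value by visit, with the stratification factor in the model, is standard and pre-specified. This stands in full, and it is why the point is only an improvement.

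**The gain may be close to nothing.** Screening can precede Day 0 by up to 42 days, or longer with approval (Section 3.1). Prohibited psychotropic drugs are washed out in between (Section 4.1), so some screening scores are taken on prior treatment. When screening is short, the two-week recall period on the CMAI form (Appendix 6) makes the two scores overlap. Either way screening may predict Week 12 less well than Day 0 does, and a fall in c from 0.50 to 0.45 removes three quarters of the benefit. This stands too, and sets the lower end of the range at zero.

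**Stronger readings that the documents do not support.**
- A reader might infer that the trial is underpowered or the estimate biased without the second score. Neither follows: the model is valid and 117 per arm is reproduced.
- A reader might take 85.1% to 86.4% as the gain over the planned analysis. That requires 16.5 to be the adjusted residual SD, whereas Section 7.1 calls it the SD of change.
- A reader might argue that Day 0 is the less trustworthy score because the NPI agitation threshold must be met there. Inclusion criterion 8 applies the same threshold at screening, so this does not separate the two scores.
- A reader might assume all three scores equally correlated, at 0.3 to 0.8, which gives a cut of 5% to 20%. Nothing in the Protocol supports that, and the washout and the recall period argue against it.

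**A bare added clause would be incomplete.** Subjects may be rescreened with all procedures repeated (Sections 3.4.3 and 3.9), and a missing covariate would drop the subject from PROC MIXED. This is a fair criticism, and the wording of the change has to deal with it.

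**Conclusion.** The point holds as a low-severity free improvement. A certified-rater CMAI is collected at screening, the model fixed in Section 7.4.1 does not use it, and using it would leave the endpoint and the validity of the analysis unchanged.

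The size rests on assumed correlations. The residual variance cut is 0% to about 10% when screening tracks Day 0 more closely than Week 12, and 3.7% in the worked case that gives screening and Day 0 equal predictive value. In that case power gains 1.3 points (85.1% to 86.4%) on one reading of the SD and about 0.8 points (93.4% to 94.2%) on the reading the Protocol states. No magnitude is claimed for the CGI-S.

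**What to change.** In Section 7.4.1 and the synopsis, add to the MMRM the interaction of screening CMAI total score with visit week. Keep change from Day 0 as the endpoint and Day 0 CMAI by visit week in the model. State two rules with it:

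- The score used comes from the screening episode that led to randomization. If that episode holds more than one CMAI, say which counts.
- A missing screening score is imputed from pre-randomization data only, for example the overall mean across arms, so that no subject is dropped.

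In Section 7.4.2, treat screening CGI-S by visit in the same way.

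The cost is short added text in the Protocol and SAP and six model parameters, one per post-baseline visit, against about 350 evaluable subjects (3 × 117 = 351). No new data are needed. If the screening score turns out uninformative, its coefficients will be near zero and only a few degrees of freedom are lost. The sample size need not change.

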7.4.2. Key Secondary Efficacy Analysis

The key secondary efficacy variable is the change from baseline to endpoint in the CGI-S score, as related to agitation. It will be analyzed by the same statistical methodology specified for the analysis of the primary efficacy variable, based on the ITT population. In order to control the overall type I error rate for this key secondary efficacy analysis, a hierarchical testing procedure will be used so that the overall experiment-wise type I error rate is maintained at 0.05. Thus, if the primary efficacy analysis for the CMAI total score (as described in [Section 7.4.1](#)) yields a statistically significant result at 0.05 (2-sided) for both of the comparisons of brexpiprazole 1 mg/day and 2 mg/day versus placebo, then the corresponding comparison for this key secondary efficacy variable (CGI-S score) will be tested at an alpha level of 0.05 (2-sided) using another hierarchical testing procedure in the order of brexpiprazole 2 mg/day versus placebo and brexpiprazole 1 mg/day versus placebo. Thus, brexpiprazole 1 mg/day versus placebo will be tested only if brexpiprazole 2 mg/day versus placebo reaches significance at 0.05 (2-sided) for this key secondary efficacy variable.

